14.1.2 Primary Objective: Sensitivity Analyses of the Primary Endpoints

The robustness of the results of the primary analysis will be evaluated by the following:

- The primary analysis will be repeated on the TCS
- The primary analysis will be repeated by subgroup "Previous treatment with DMDs" on the FAS.

Analysis (Analysis Set)	Derivation	Statistical Analysis Methods	Missing data handling
	oint: Proportion of participants se of cladribine tablets	with NEDA-3 during Year 3 Visit a	and Year 4 Visit Period after
Sensitivity (TCS)	Same as in the Primary Analysis (see Section 14.1.1)	Same as in the Primary Analysis (see Section 14.1.1)	Same as in the Primary Analysis (see Section 14.1.1)
Sensitivity (FAS by subgroup "Previous treatment with DMDs")	Same as in the Primary Analysis (see Section 14.1.1)	Same as in the Primary Analysis (see Section 14.1.1) with KM estimates reported by subgroup.	Same as in the Primary Analysis (see Section 14.1.1)
Sensitivity (FAS)	Crude percentages and time to event with descriptive summaries for qualifying relapse, 6MCDP, or MRI activity and NEDA	A descriptive summary of number and proportion of participants with event A descriptive summary of time to earliest event (overall and by type of event, i.e., qualifying relapse, 6MCDP, or MRI activity).	Missings will be presented in a separate category

14.2 Secondary Endpoints

14.2.1 No Evidence of Disease Activity

As a secondary analysis, NEDA-3 during the following Periods (see definition in Section 9.6) will be analyzed similarly as in the primary analysis using the KM method:

Year 3 Visit Period

- Start date: end date of M24 Visit (see definition in Section 14.1.1) + 1
- Event date: same as in Section 14.1.1 accounting for events started during Year 3 Visit Period only
- Censoring date: the minimum of the scan date of the last available MRI during Year 3 Visit Period, the assessment date of the last available EDSS during Year 3 Visit Period, and the end date of Year 3 Visit Period (see definition in Section 9.6)

Year 4 Visit Period

- Start date: end date of M36 Visit + 1
- Event date: same as in Section 14.1.1 accounting for events started during Year 4 Visit Period only

• Censoring date: the minimum of the scan date of the last available MRI during Year 4 Visit Period, the assessment date of the last available EDSS during Year 4 Visit Period, and the Extension Study completion/discontinuation date

After start of study medication until end of Year 3 Visit Period

- Start date: date of Day 1 as defined in Section 9.5
- Event date: The event date will be defined as the minimum of
 - o the onset date of the first qualifying relapses during the Parent and Extension Study Period
 - o the start date of the first 6MCDP during the Parent and Extension Study Period
 - o the scan date of the first MRI during the Parent and Extension Study Period where at least one T1 Gd+ lesion or at least one active T2 lesion (see Section 9.8 for definition) is identified,

accounting for events started during "After start of study medication until end of Year 3 Visit Period" only.

• Censoring date: the minimum of the scan date of the last available MRI during "After start of study medication until end of Year 3 Visit Period", the assessment date of the last available EDSS during "After start of study medication until end of Year 3 Visit Period", and the end date of "After start of study medication until end of Year 3 Visit Period" (see definition in Section 9.6)

After start of study medication until end of Year 4 Visit Period (i.e. Parent and Extension Study Period)

- Start date: date of Day 1 as defined in Section 9.5
- Event date: same as for "After start of study medication until end of Year 3 Visit Period" accounting for events started during "After start of study medication until end of Year 4 Visit Period"
- Censoring date: the minimum of the scan date of the last available MRI during "After start of study medication until end of Year 4 Visit Period", the assessment date of the last available EDSS during "After start of study medication until end of Year 4 Visit Period", and the Extension Study completion/discontinuation date

Year 3 Visit Period (or Year 4 Visit Period) among participants with NEDA-3 during Course 1 Treatment Period (or Course 2 Treatment Period)

Analysis of NEDA-3 during the Year 3 Visit Period and analysis of NEDA-3 during the Year 4 Visit Period as defined above will be repeated, respectively, on the subset of participants with

NEDA-3 during Course 1 Treatment Period and on the subset of participants with NEDA-3 during Course 2 Treatment Period.

NEDA-3 during Course 1 Treatment Period is defined similarly as in Section 14.3.12 of MAGNIFY MS IAP version 3.0 with just Treatment Period replaced by Course 1 Treatment Period and the following definition for MRI activity:

- Yes: At least one T1 Gd+ at any scan assigned to Month 6, Month 12 Visit, or at least one active T2 during any of the following Periods: Baseline Month 6, Month 6 Month 12.
- No: T1 Gd+ = 0 at all scans assigned to Month 6, Month 12 Visit that have a value and at least one T1 Gd+ value from Month 6 or Month 12 Visit is available, and all active T2 = 0 during any of the following Periods: Baseline Month 6, Month 6 Month 12 that have a value and at least one active T2 value from Periods Baseline Month 6 or Month 6 Month 12 is available.
- Unknown: Otherwise.

NEDA-3 during Course 2 Treatment Period is defined similarly as in Section 14.3.12 of MAGNIFY MS IAP version 3.0 with just Treatment Period replaced by Course 2 Treatment Period and the following definition for MRI activity:

- Yes: At least one T1 Gd+ at any scan assigned to Month 18, Month 24 Visit, or at least one active T2 during any of the following Periods: Month 12 Month 18, Month 18 Month 24.
- No: T1 Gd+ = 0 at all scans assigned to Month 18, Month 24 Visit that have a value and at least one T1 Gd+ value from Month 18 or Month 24 Visit is available, and all active T2 = 0 during any of the following Periods: Month 12 Month 18, Month 18 Month 24 that have a value and at least one active T2 value from Periods Month 12 Month 18, Month 18 Month 24 is available.
- Unknown: Otherwise.

Analysis (Analysis Set)	Derivation	Statistical Analysis Methods	Missing data handling
Secondary end	point: Proportion of participants	s with NEDA-3 during Year 3 V	isit Period
Secondary (FAS)	Time to event: [event date or censoring date as applicable – start date + 1]/30.4375 for	Same as in the primary analysis (see Section 14.1.1 and for subgroup analysis	Same as in the primary analysis (see Section 14.1.1)
Secondary (FAS by subgroup "Previous treatment with DMDs")	NEDA-3 events started during the Year 3 Visit Period	see Section 14.1.2)	

Analysis (Analysis Set)	Derivation	Statistical Analysis Methods	Missing data handling
Secondary (FAS for subset "participants with NEDA-3 during Course 1 Treatment Period") Secondary (FAS for subset "participants with NEDA-3			
during Course 2 Treatment Period")			
Secondary end	point: Proportion of participants	s with NEDA-3 during Year 4 V	isit Period
Secondary (FAS) Secondary (FAS by subgroup "Previous treatment with DMDs") Secondary (FAS for subset "participants with NEDA-3 during Course 1 Treatment Period") Secondary (FAS for subset "participants with NEDA-3 during Course 2 Treatment Period")	Time to event: [event date or censoring date as applicable – start date + 1]/30.4375 for NEDA-3 events started during the Year 4 Visit Period	Same as in the primary analysis (see Section 14.1.1 and for subgroup analysis see Section 14.1.2)	Same as in the primary analysis (see Section 14.1.1)
Secondary endpoint: Proportion of participants with NEDA-3 during "After start of study medication until end of Year 3 Visit Period"			
Secondary (FAS)			Same as in the primary analysis (see Section 14.1.1)

Analysis (Analysis Set)	Derivation	Statistical Analysis Methods	Missing data handling
Secondary (FAS by subgroup "Previous treatment with DMDs")	Time to event: [event date or censoring date as applicable – start date + 1]/30.4375 for NEDA-3 events started during the "After start of study medication until end of Year 3 Visit Period"	Same as in the primary analysis (see Section 14.1.1 and for subgroup analysis see Section 14.1.2)	
Secondary (FAS)	Crude percentages and time to event with descriptive summaries for qualifying relapse, 6MCDP, or MRI activity and NEDA	A descriptive summary of number and proportion of participants with event A descriptive summary of time to earliest event (overall and by type of event, i.e., qualifying relapse, 6MCDP, or MRI activity).	Missings will be presented in a separate category
Secondary end end of Year 4 V	point: Proportion of participants isit Period"	s with NEDA-3 during "After st	tart of study medication until
Secondary (FAS) Secondary (FAS by subgroup "Previous treatment with DMDs")	Time to event: [event date or censoring date as applicable – start date + 1]/30.4375 for NEDA-3 events started during the "After start of study medication until end of Year 4 Visit Period"	Same as in the primary analysis (see Section 14.1.1 and for subgroup analysis see Section 14.1.2)	Same as in the primary analysis (see Section 14.1.1)
Secondary (FAS)	Crude percentages and time to event with descriptive summaries for qualifying relapse, 6MCDP, or MRI activity and NEDA	A descriptive summary of number and proportion of participants with event A descriptive summary of time to earliest event (overall and by type of event, i.e., qualifying relapse, 6MCDP, or MRI activity).	Missings will be presented in a separate category

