5.1 Inclusion Criteria

Participants are eligible to be included in the study only if all the following criteria apply:

1. Participants of the MAGNIFY MS trial who received at least a single dose of cladribine tablets during the MAGNIFY MS trial and data on MRI is available/acquired from at least parent study Month 18 or Month 24 visit and EDSS and relapse from parent study Month 24 visit.

Informed Consent

2. Capable of giving signed informed consent, as indicated in Appendix 2, which includes compliance with the requirements and restrictions listed in the informed consent form (ICF) and this protocol.

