Period 12.1 (p_{12.1}) is defined as the Period between Baseline to Month 12 MRI scans,

Period 12.2 (p_{12.2}) is defined as the Period between Month 12 to Month 24 MRI scans,

Period 12.3 (p_{12.3}) is defined as the Period between Month 24 to Month 36 MRI scans,

Period 12.4 (p_{12.4}) is defined as the Period between Month 36 to Month 48 MRI scans.

2-Year Period:

Period 24.1 (p_{24.1}) is defined as the Period between Baseline to Month 24 MRI scans.

3-Year Period:

Period 36.1 (p_{36.1}) is defined as the Period between Baseline to Month 36 MRI scans.

4-Year Period:

Period 48.1 (p_{48.1}) is defined as the Period between Baseline to Month 48 MRI scans.

Sequential Visit Periods:

For p_{100.0}, p_{100.1}, p_{100.2}, p_{100.3}, p_{100.6}, p_{100.12}, p_{100.15}, p_{100.18}, p_{100.24}, see Section 9 of MAGNIFY MS IAP version 3.0.

Period 100.36 ($p_{100.36}$) is defined as the Period between Month 24 to Month 36 (equivalent to $p_{12.3}$) MRI scans.

Period 100.48 ($p_{100.48}$) is defined as the Period between Month 36 to Month 48 (equivalent to $p_{12.4}$) MRI scans.

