 New T1 Gd+ lesion count = T1 Gd+ lesions count from the MRI at Month 36 / Month 48 Visit due to longer periods

For example: New T1 Gd+ lesion count of the Period between Month 24 and Month 36 (p12.3) is equal to T1 Gd+ lesion count from the MRI at Month 36 Visit.

Active T2 lesion count

As the active (i.e., the new or enlarging) T2 lesion count depends on the length of the Period, it will be presented as reported (non-standardized) and annualized (standardized to 1 years (365.25 days)):

- Period length (days) = MRI date at end of Period MRI date at start of Period +1,
- Annualized active T2 lesion count (by Period) = Total number of active T2 lesions per Period * 365.25/ Period length.

The following types of T2 lesions are defined per Period (standardized and non-standardized):

- Total new T2 lesion count =
 - Total number of new T2 lesions with T1 Gd+
 - + Total number of new T2 lesions without T1 Gd+
- Total enlarging T2 lesion count =

Total number of enlarging T2 lesions with T1 Gd+

- + Total number of enlarging T2 lesions without T1 Gd+
- Total active T2 lesion count =

Total new T2 lesion count

+ Total enlarging T2 lesion count

Note: the number of new or enlarging T2 (with and without T1 Gd+) will be provided by central reading for each of the Periods including the Sequential Visit Periods.

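### SAP 14.2.1 accepts only half-year T2 comparisons for Course 1 and Course 2, so missing scans can drop participants with a documented clean year from the remaining-NEDA-3 subsets

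*SAP*

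**What the plan says.** SAP 14.2.1 defines MRI activity in each treatment course from two scans (Month 6 and Month 12 for Course 1, Month 18 and Month 24 for Course 2) and two half-year T2 Periods.

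- **Yes** in Course 1 follows from "At least one T1 Gd+ at any scan assigned to Month 6, Month 12 Visit", or from an active T2 lesion in either half-year Period.
- **No** needs every available value to be zero, with two minimum conditions. For Gd+, "at least one T1 Gd+ value from Month 6 or Month 12 Visit is available". For T2, "at least one active T2 value from Periods Baseline Month 6 or Month 6 Month 12 is available". The Course 2 T2 condition is "at least one active T2 value from Periods Month 12 Month 18, Month 18 Month 24 is available".
- The remainder is "Unknown: Otherwise".

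SAP 9.6 also defines yearly Periods. For p12.1, the Period "is defined as the Period between Baseline to Month 12 MRI scans"; p12.2 runs from Month 12 to Month 24. SAP 9.8 says that new or enlarging T2 counts "will be provided by central reading for each of the Periods including the Sequential Visit Periods". Protocol 5.1 admits participants if "data on MRI is available/acquired from at least parent study Month 18 or Month 24 visit", so either Course 2 scan may be absent. SAP 8.2 and 14.2.1 use the resulting subsets for the Year 3 and Year 4 analyses of participants remaining NEDA-3.

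**The concern.** The rule treats two kinds of incomplete imaging unevenly. With the mid-year scan missing, neither half-year comparison can be formed from adjacent scans, so a participant whose whole year is covered by one T2 comparison has no accepted T2 value. With the year-end scan missing, one half-year comparison is enough for No over the whole course, although the second half was not imaged. The Kaplan-Meier analyses of the same SAP are stricter on this point: event-free participants are censored no later than their last MRI and earn no credit after it.

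At stake is who enters the denominators of one secondary endpoint, the proportion remaining NEDA-3 in Year 3 or Year 4 among those with NEDA-3 in Course 1 or Course 2. Some participants documented as clean can be left out, and a few with unseen activity can be let in.

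**Working it through.** The plan states no figure on this point, so there is none to reproduce. The check has two parts.

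**1. The rule applied to each scan pattern.** Start, mid and end are Baseline, Month 6 and Month 12 (Course 1) or Month 12, Month 18 and Month 24 (Course 2). No Gd+ lesion is seen on any available scan.

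| Scans present | No T2 activity | T2 activity in first half only | T2 activity in second half only |
|---|---|---|---|
| start, mid, end | No | Yes | Yes |
| start, mid | No | Yes | No |
| start, end | Unknown | Unknown | Unknown |
| mid, end | No | No | Yes |
| any single scan, or none | Unknown | Unknown | Unknown |

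In the third row the Gd+ condition is met by the year-end scan alone; only the T2 condition fails. A Gd+ lesion on that scan would give Yes. If p12.1 or p12.2 counted as T2 evidence, this row would read No, Yes, Yes and no other row would change.

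**2. Size, under assumptions.** From the Protocol synopsis: 200 to 220 evaluable participants, taken as N = 210. Assumed, because the documents do not give them: each mid-year and year-end scan missing independently with probability m = 3%, 5% or 10%; start scan present; 12-month MRI activity a = 20%, 30% or 40% at a constant rate. The probability that a half-year is clean is then s = √(1−a) = 0.894, 0.837 or 0.775.

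- One named scan missing, the other present: N·m(1−m) = 6.1, 10.0, 18.9. This applies to each of the two patterns.
- Scored No on the first half alone: N·m(1−m)·s. Lowest 6.1 × 0.775 = 4.7; highest 18.9 × 0.894 = 16.9.
- Of these, active in the unseen half: N·m(1−m)·s(1−s). Lowest 6.1 × 0.894 × 0.106 = 0.6; highest 18.9 × 0.775 × 0.225 = 3.3.
- Mid-year missing with a clean full-year comparison, left Unknown: N·m(1−m)(1−a). Lowest 6.1 × 0.6 = 3.7; highest 18.9 × 0.8 = 15.1.

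In the middle case (m = 5%, a = 30%) the last three figures are 8.3, 1.4 and 7.0.

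Relative to everyone scored No, N[(1−m)²(1−a) + m(1−m)s]:

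- Unseen activity is 0.6/163.5 = 0.4% (m = 3%, a = 20%) to 3.3/116.7 = 2.8% (m = 10%, a = 40%).
- The clean participants left Unknown would add 3.7/123.3 = 3.0% (m = 3%, a = 40%) to 15.1/153.0 = 9.9% (m = 10%, a = 20%).

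A second set of assumptions (N = 200, 2-10% missing, T2 activity 5-20% per half-year) gives 3.1-17.1 scored No on the first half alone, 0.2-2.9 of them with unseen activity, and 2.5-16.2 clean participants left Unknown.

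**The case against.** The strongest reply is that this is an ordinary available-data rule. SAP 9.7 evaluates data as observed without imputation by default, and the descriptive MRI rule in SAP 14.1.1 calls the whole Extension Study Period No on a single post-Baseline MRI. Demanding full coverage for No in Course 1 and Course 2 would be stricter than that. This stands, so full coverage belongs in a sensitivity analysis. It does not explain why a full-year count that the SAP says is supplied should be disregarded.

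A reader might also infer that the rule lets known T2 activity into the subsets, because a positive p12.1 gives Unknown instead of Yes. The documents do not support that. The classification serves only to select participants with NEDA-3, and on the natural reading Unknown and Yes are both left out. Recoding one to the other changes no denominator.

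The parent analysis plan is not among the documents. SAP 14.2.1 takes the composite from its Section 14.3.12, SAP 9.6 refers to it for the parent-study sequential Periods, and SAP 9 keeps parent rules in force unless replaced. A parent rule for comparing across a missing scan cannot be excluded. On the other side, SAP 14.2.1 explicitly writes its own MRI-activity definition and mentions no such rule.

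Finally, the number wrongly admitted is small, and leaving out clean participants costs mainly precision; it biases the estimate only if mid-year missingness is related to outcome. Both points stand.

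**Conclusion.** The gap is plain in the text of SAP 14.2.1, and its reach is limited. If scans are missing, the subsets can be misclassified. It would go too far to say that they are: the documents give no parent-study missing-scan rate, and anyone with all three scans is scored correctly. The primary endpoint does not use these classifications, and the study is single-arm and exploratory.

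Under the stated assumptions, about 5-17 participants per course are scored No on the first half alone, with 0.6-3.3 having unseen activity, before any are removed for relapse or disability progression. A similar number (6-19, less any with Gd+ at year-end) are left Unknown despite a full-year comparison, and 4-15 of all those lacking only the mid-year scan have a clean one. The gain from a change lies mainly in recovering these clean participants. The figures rest on independent missingness, a constant activity rate and a present start scan. The requirement in Protocol 5.1 that Month 18 or Month 24 be available hardly alters them for Course 2: both missing would be 0.10 × 0.10 = 1% at most.

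**What to change.** In SAP 14.2.1, when a half-year T2 value is missing, accept the active T2 count from p12.1 (Course 1) or p12.2 (Course 2) as T2 evidence for Yes or No. Participants with both half-year values keep their classification.

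Tabulate participants by scan pattern for each course, so that the real size replaces the assumed one. Add a sensitivity analysis in which No requires coverage to the end of the course: T2 activity of 0 in both half-year Periods or in the full-year Period, and Gd+ of 0 at the year-end scan. If the parent analysis plan already states how to compare across a missing scan, cite that rule in 14.2.1.

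The cost is a few lines of SAP text and a small derivation change using counts that SAP 9.8 says are supplied. In the sensitivity analysis, participants without a year-end scan, and those without a start scan, move from No to Unknown, so that subset is smaller.

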14.2.2 Time to First Disease Activity

Time to first disease activity is defined as the time to first occurrence of either qualifying relapse, or 6MCDP, or new or enlarging T2-hyperintense lesions (active T2 lesions), or new T1 Gd+ lesions. This will be evaluated for the following Periods with corresponding start dates defined below:

- Extension Study Period
 - Start date for time to first disease activity: end date of M24 Visit + 1 (as defined in Section 14.1.1)
- Parent and Extension Study Period

o Start date for time to first disease activity: date of Day 1 (as defined in Section 9.5)

Since events described above are the same events as in NEDA-3 definition, the event date will be defined the same as in Sections 14.1.1 or 14.2.1, accounting for only events started during the above Periods, respectively. If the participant did not experience any disease event during a Period, the minimum of the scan date of the last available MRI during this Period, the assessment date of the last available EDSS during this Period, and the Extension Study completion/discontinuation date will be used as the censoring date.

Time to first disease activity (in months) will be calculated as [event date or censoring date as applicable – start date of the Period + 1]/30.4375 and the 5%, 10%, 15%, 25% percentile and median time to first disease activity will be estimated using the KM method along with the 95% CI.

Analysis (Analysis Set)	Derivation	Statistical Analysis Methods	Missing data handling
Secondary er	ndpoint: Time from M24 Visit to	o first disease activity	
Secondary (FAS)	Time to event: [event date or censoring date as applicable – start date + 1]/30.4375 for disease activities started during Extension Study Period	KM time-to-event: 5%, 10%, 15%, 25% percentiles and Median time to disease activity will be estimated as per the KM method and reported along with the corresponding 95% CI.	Same as Section 14.1.1
Secondary (FAS by subgroup "Previous treatment with DMDs")	Same as above	Same as above with KM estimates reported by subgroup.	Same as Section 14.1.1
Secondary er	ndpoint: Time from initial dose	of cladribine tablets to first diseas	e activity
Secondary (FAS)	Time to event: [event date or censoring date as applicable – start date + 1]/30.4375 for	Same as above.	Same as above.
Secondary (FAS by subgroup "Previous treatment with DMDs")	disease activities started during Parent and Extension Study Period		

14.2.3 Time to MRI Activities, 6MCDP, Qualifying Relapse and Treatment Start with Other DMDs

Time (in months) from the initial dose of cladribine tablets (i.e. start date = date of Day 1 as defined in Section 9.5) to the following events will be calculated as [event date or censoring date as applicable – start date + 1]/30.4375, and analyzed similarly as in Section 14.2.2 using the KM method.

- first new or enlarging T2 lesion
 - Event date: the scan date of the first MRI during the Parent and Extension Study Period where at least one active T2 lesion (see Section 9.8 for definition) is identified
 - Censoring date: participants with no active T2 lesion identified at any scans during the Parent and Extension Study Period will be censored at the scan date of the last available MRI during this Period
- first new T1 Gd+ lesion
 - Event date: the scan date of the first MRI during the Parent and Extension Study Period where at least one new T1 Gd+ lesion (see Section 9.8 for definition) is identified
 - Censoring date: participants with no new T1 Gd+ lesion identified at any scans during the Parent and Extension Study Period will be censored at the scan date of the last available MRI during this Period
- first 6MCDP, as measured by EDSS
 - Event date: the start date of the first 6MCDP during the Parent and Extension Study Period
 - 6MCDP during the Parent and Extension Study Period will be defined similarly as in Section 14.1.1 with just Extension Study Period replaced by Parent and Extension Study Period.
 - Censoring date: participants with no 6MCDP started during the Parent and Extension Study Period will be censored at the assessment date of the last available EDSS during this Period
- first qualifying relapse
 - Event date: the onset date of the first qualifying relapse during the Parent and Extension Study Period

 Censoring date: participants with no qualifying relapse reported during the Parent and Extension Study Period will be censored at the Extension Study completion/discontinuation date

Time (in months) from M24 Visit (i.e. start date = end date of M24 Visit + 1) to the following events will be calculated as (event date or censoring date as applicable – start date + 1/30.4375, and analyzed similarly as in Section 14.2.2 using the KM method.

- first new or enlarging T2 lesion
 - Event date: the scan date of the first MRI during the Extension Study Period where at least one active T2 lesion (see Section 9.8 for definition) is identified
 - Censoring date: participants with no active T2 lesion identified at any scans during the Extension Study Period will be censored at the scan date of the last available MRI during this Period
- first new T1 Gd+ lesion
 - Event date: the scan date of the first MRI during the Extension Study Period where at least one new T1 Gd+ lesion (see Section 9.8 for definition) is identified
 - Censoring date: participants with no new T1 Gd+ lesion identified at any scans during the Extension Study Period will be censored at the scan date of the last available MRI during this Period
- first 6MCDP, as measured by EDSS
 - Event date: the start date of the first 6MCDP during the Extension Study Period (see definition in Section 14.1.1)
 - Censoring date: participants with no 6MCDP started during the Extension Study Period will be censored at the assessment date of the last available EDSS during this Period
- first qualifying relapse
 - Event date: the onset date of the first qualifying relapse during the Extension Study Period
 - Censoring date: participants with no qualifying relapse reported during the Extension Study Period will be censored at the Extension Study completion/discontinuation date
- treatment start with other DMDs

- Event date: the start date of the first other DMDs used during the Extension Study Period
- Censoring date: participants who did not use any other DMDs during the Extension Study Period will be censored at the Extension Study completion/discontinuation date

A recurrent event analysis will be performed on all qualifying relapses using the Mean Cumulative Function (MCF) method, where MCF(t) represents the mean cumulative number of relapses up to time t. The MCF estimate for recurrent events will be calculated and plotted for all qualifying relapses. The MCF Nelson estimates will be presented for every month along with their 95% CIs. The increase in MCF in each month, defined as MCF(t) - MCF(t-1) will also be displayed.

Time (in months) from the initial dose of cladribine tablets (i.e. start date = date of Day 1 as defined in Section 9.5) to each event and to censoring (as defined below) will be calculated as [event date or censoring date – start date + 1/30.4375, and analyzed using the MCF method.

- recurrent qualifying relapse
 - Event date: the onset date of each qualifying relapse during the Parent and Extension Study Period
 - Censoring date: all participants with no qualifying relapse reported during the Parent and Extension Study Period will be censored at the Extension Study completion/discontinuation date

Time (in months) from M24 Visit (i.e. start date = end date of M24 Visit + 1) to each event and to censoring (as defined below) will be calculated as [event date or censoring date – start date + 1/30.4375, and analyzed using the MCF method.

[figure not shown]
- recurrent qualifying relapse
 - Event date: the onset date of each qualifying relapse during the Extension Study Period
 - Censoring date: all participants with no qualifying relapse reported during the Extension Study Period will be censored at the Extension Study completion/discontinuation date

Analysis (Analysis Set)	Derivation	Statistical Analysis Methods	Missing data handling	
Secondary endpoint: Time from the initial dose of cladribine tablets to MRI activities, 6MCDP, and qualifying relapse				
Secondary (FAS)		Same as in Section 14.2.2	Same as in Section 14.2.2	

[figure not shown]
Analysis	Derivation	Statistical Analysis Methods	Missing data handling
(Analysis Set)			
Secondary (FAS by subgroup "Previous treatment with DMDs")	Time to event: [event date or censoring date as applicable – start date + 1]/30.4375 for first active T2 lesion identified during the Parent and Extension Study Period		
Secondary (FAS)	Time to event: [event date or censoring date as applicable – start date + 1]/30.4375 for first T1		
Secondary (FAS by subgroup "Previous treatment with DMDs")	Gd+ lesion identified during the Parent and Extension Study Period		
Secondary (FAS)	Time to event: [event date or censoring date as applicable – start date + 1]/30.4375 for first 6MCDP started during the Parent and Extension Study Period		
Secondary (FAS by subgroup "Previous treatment with DMDs")			
Secondary (FAS)	Time to event: [event date or censoring date as applicable – start date + 1]/30.4375 for first		
Secondary (FAS by subgroup "Previous treatment with DMDs")	qualifying relapse reported during the Parent and Extension Study Period		
Secondary (FAS)			Same as Section 14.2.2

[figure not shown]
Analysis	Derivation	Statistical Analysis Methods	Missing data handling
(Analysis Set)			
Secondary (FAS by subgroup "Previous treatment with DMDs")	Time to event: [event date – start date + 1]/30.4375 for each qualifying relapse reported during the Parent and Extension Study Period and [censoring date – start date + 1]/30.4375 with censoring at Extension Study completion/discontinuation date for all participants	The MCF estimate for recurrent events will be calculated and plotted for all qualifying relapses. The MCF Nelson estimates will be presented for every month along with their 95% CIs. The increase in MCF in each month, defined as MCF(t) - MCF(t-1) will also be displayed.	
Secondary e with other D	endpoint: Time from M24 Visit to M MDs	RI activities, 6MCDP, qualifying	relapse, and treatment start
Secondary (FAS)	Time to event: [event date or censoring date as applicable – start date + 1]/30.4375 for first	Same as in Section 14.2.2	Same as in Section 14.2.2
Secondary (FAS by subgroup "Previous treatment with DMDs")	active T2 lesion identified during the Extension Study Period		
Secondary (FAS)	Time to event: [event date or censoring date as applicable – start date + 1]/30.4375 for first T1		
Secondary (FAS by subgroup "Previous treatment with DMDs")	Gd+ lesion identified during the Extension Study Period		
Secondary (FAS)	Time to event: [event date or censoring date as applicable – start date + 1]/30.4375 for first		
Secondary (FAS by subgroup "Previous treatment with DMDs")	6MCDP started during the Extension Study Period		
Secondary (FAS)			

Analysis (Analysis Set)	Derivation	Statistical Analysis Methods	Missing data handling
Secondary (FAS by subgroup "Previous treatment with DMDs")	Time to event: [event date or censoring date as applicable – start date + 1]/30.4375 for first qualifying relapse reported during the Parent and Extension Study Period		
Secondary (FAS)	Time to event: [event date or censoring date as applicable – start date + 1]/30.4375 for other		
Secondary (FAS by subgroup "Previous treatment with DMDs")	DMDs started during the Extension Study Period		
Secondary (FAS)	Time to event: [event date – start date + 1]/30.4375 for each qualifying relapse reported during the	The MCF estimate for recurrent events will be calculated and plotted for all qualifying relapses. The MCF	Same as Section 14.2.2
Secondary (FAS by subgroup "Previous treatment with DMDs")	Extension Study Period and [censoring date – start date + 1]/30.4375 with censoring at Extension Study completion/discontinuation date for all participants	Nelson estimates will be presented for every month along with their 95% CIs. The increase in MCF in each month, defined as MCF(t) - MCF(t-1) will also be displayed.	

[figure not shown]

[figure not shown]

[figure not shown]
Mavenclad® MAGNIFY Extension MS700568_0157 Version 2.0

[figure not shown]

[figure not shown]

[figure not shown]

Mavenclad® MAGNIFY Extension MS700568_0157 Version 2.0

[figure not shown]

[figure not shown]

[figure not shown]

[figure not shown]

[figure not shown]

[figure not shown]

[figure not shown]

[figure not shown]
Mavenclad® MS700568_0157 MAGNIFY Extension Version 2.0

Mavenclad® MS700568_0157 MAGNIFY Extension Version 2.0

Mavenclad® MS700568_0157 MAGNIFY Extension Version 2.0

15 Safety Analyses

This section includes specifications for summarizing safety endpoints that are common across clinical studies such as adverse events, laboratory tests and vital signs.

Safety analyses will be done on the SAF and reflect data collected during the Extension Study Period.

